    - Bone marrow blasts decreased by  $\geq 50\%$  over pretreatment but still  $> 5\%$
    - Cellularity and morphology not relevant
  - Marrow CR: For subjects to be classified as being in marrow CR at a post-baseline visit, they must have all of the following for a minimum of 4 weeks:
    - Bone marrow:  $\leq 5\%$  myeloblasts and decrease by  $\geq 50\%$  over pretreatment
      - Peripheral blood: if HI responses, they will be noted in addition to marrow CR
  - Hematologic Improvement (HI): For subjects to be classified as having hematologic improvement (HI) at a post-baseline visit, they must have 1 measurement of the following, maintained for at least 8 weeks without ongoing cytotoxic therapy:
    - HI – erythroid:

- Hemoglobin increase of  $\geq 1.5$  g/dL or
- For RBC transfusions performed for hemoglobin  $\leq 9.0$  g/dL: reduction in RBC units transfused in 8 weeks by  $\geq 4$  units compared to the number of units transfused in the 8 weeks prior to treatment
- HI – platelets:
  - For pre-treatment platelet count of  $>20 \times 10^9$  /L platelet, absolute increase of  $\geq 30 \times 10^9$  /L
  - For pre-treatment platelet count of  $< 20 \times 10^9$  /L, platelet absolute increase of  $> 20 \times 10^9$  /L and  $\geq 100\%$  increase from pre-treatment level
- HI – neutrophils:
  - Neutrophil count increase of  $\geq 100\%$  from pre-treatment level and an absolute increase of  $> 0.5 \times 10^9$  /L
- Relapse after CR or PR: For subjects to be classified as relapsing after CR or PR requires at least one of:
  - Return to pre-treatment bone marrow blast percentage
  - Decrement of  $\geq 50\%$  from maximum response levels in granulocytes or platelets
  - Transfusion dependence or hemoglobin level  $\geq 1.5$  g/dL lower than prior to therapy
- Stable Disease (SD): For subjects to be classified as having Stable Disease (SD), they must fail to achieve at least PR but show no evidence of progression for  $>8$  weeks
- Progressive Disease (PD): For subjects to be classified as having Progressive Disease (PD), they must show blast level increases depending on prior levels as follows:
  - For patients with:
    - $<5\%$  blasts:  $\geq 50\%$  increase in blasts to  $> 5\%$  blasts
    - $5\%-10\%$  blasts:  $\geq 50\%$  increase to  $> 10\%$  blasts
    - $10\%-20\%$  blasts:  $\geq 50\%$  increase to  $> 20\%$  blasts
    - $20\%-30\%$  blasts:  $\geq 50\%$  increase to  $> 30\%$  blasts
  - Or any of the following:

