    - At least 50% decrement from maximum remission/response in granulocytes or platelets
    - Reduction in Hgb by  $\geq 2$  g/dL from maximum remission/response
    - Transfusion dependence: RBC or platelet transfusion after a previous CR, BM CR, PR, or HI response
    - A relapse from CR, BM CR, PR, or HI is also considered PD

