### 5.1.9 Secondary Efficacy Endpoint: Duration of Response

Duration of response (DOR) for AML includes duration of CRc, duration of CR/CRh, duration of CRh, duration of CR, and duration of response (i.e., CRc + PR). DOR is defined as the time from the date of first response until the date of documented relapse.

Duration of response for MDS includes duration of CR and duration of response (i.e., CR + BM CR + PR). DOR is defined as the time from the date of first response date until the date of documented relapse.

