### 5.1.11 Other Efficacy Endpoint: Transfusion Status

Transfusion status (independent vs. dependent) at baseline period and post-baseline period are defined in the following for subjects who took at least one dose of study drug:

Baseline transfusion status:

- Baseline period is defined as the period from 28 days prior to first dose until 28 days after the first dose. For subjects who are on treatment <28 days, baseline period is from the 28 days prior to first dose until the end of treatment.
- Subjects are considered baseline transfusion independent if there is no RBC or platelet transfusions within the baseline period; otherwise, the subject is baseline transfusion dependent.

Post-baseline transfusion status:

- Post-baseline period is defined as the period from 29 days after first dose date until the end of Observation Period 2.

- For subjects who are on study  $\geq 84$  days, subjects are considered post-baseline transfusion independent if there are 56 consecutive days without any RBC or platelet transfusion within post-baseline period.
- For subjects who are on study  $> 28$  days but  $< 84$  days, if there is no RBC or platelet transfusion within post-baseline period, post-baseline transfusion status is not evaluable.
- For subjects who are on study  $\leq 28$  days, post-baseline transfusion status is not evaluable.
- Otherwise, the subject is considered post-baseline transfusion dependent.

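### SAP 5.1.1 dates MDS progression at any transfusion after marrow CR or HI, although neither requires transfusion independence, so the listed PFS dates are wrong for responders still being transfused

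*SAP*

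**What the plan says.** The MDS definition of progressive disease is in SAP 5.1.1, in the text after the AML classification table. It gives blast-increase rules and then, under "Or any of the following", further criteria that each suffice alone. One is labelled transfusion dependence and reads "RBC or platelet transfusion after a previous CR, BM CR, PR, or HI response". Another adds: "A relapse from CR, BM CR, PR, or HI is also considered PD".

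The same section defines the responses named there:

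- **Marrow CR** rests on marrow blasts alone: at most 5%, with at least a 50% decrease, held for 4 weeks. On peripheral blood it says only "if HI responses, they will be noted in addition to marrow CR".
- **HI-platelets and HI-neutrophils** are defined on counts, with no transfusion condition.
- **HI-erythroid** can be met by a haemoglobin rise or by a reduction of at least 4 "units compared to the number of units transfused in the 8 weeks prior to treatment".

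The relapse rule in 5.1.1 also lists transfusion dependence, but its scope is narrower: "For subjects to be classified as relapsing after CR or PR requires at least one of". Protocol 7.1.1.2 gives the same marrow CR and HI definitions and the same CR/PR-only relapse rule. It contains no MDS progression definition.

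SAP 5.1.10 uses progression as a PFS event (MDS only), and SAP 6.4.2.6 reports PFS in a listing only. SAP 5.1.11 defines transfusion status differently: "subjects are considered post-baseline transfusion independent if there are 56 consecutive days without any RBC or platelet transfusion within post-baseline period", for subjects on study at least 84 days.

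**The concern.** A progression criterion should record worsening. Transfusion is a sign of worsening in someone who did not need it, or who stopped needing it as part of the response. The criterion is also applied to marrow CR and HI, which can be reached with the pre-treatment transfusion need intact or only reduced. In those subjects the next routine transfusion meets the definition even though the marrow, the blood counts and the transfusion rate are no worse than when the response was recorded.

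For HI by transfusion reduction the rule works against itself. The remaining transfusions are counted to show that HI was achieved, and transfusions of the same kind then end it. What is at stake is whether the PFS dates listed for MDS subjects mean what a reader will take them to mean.

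**Working it through.** The plan states no figure on this point, so there is nothing to reproduce. The check compares the definitions and then does the unit arithmetic for HI-erythroid.

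**1. Does the response require transfusion independence?**

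| Response | Transfusion condition in SAP 5.1.1 | Transfusion afterwards counts as progression? |
|---|---|---|
| Marrow CR | None | Yes |
| HI-platelets, HI-neutrophils | None | Yes |
| HI-erythroid by transfusion reduction | At least 4 fewer red-cell units per 8 weeks; zero not required | Yes |

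**2. How much transfusion does HI-erythroid allow?** Let U be the red-cell units in the 8 weeks (56 days) before treatment. HI is met with up to m = U − 4 units in 8 weeks. If units are given singly and evenly, the mean interval is 56/m days.

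| U before | m still allowed | Mean interval (days) |
|---|---|---|
| 4 | 0 | none |
| 5 | 1 | 56 |
| 6 | 2 | 28 |
| 8 | 4 | 14 |
| 12 | 8 | 7 |

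Among subjects who qualify by this route at the minimum reduction, only one who starts at exactly 4 units must reach zero. A subject going from 8 to 4 units is a responder who can expect a unit about every 14 days, and so is progressed about two weeks after HI is established. If units are given two at a time, that is 4/2 = 2 episodes per 8 weeks, or 56/2 = 28 days apart.

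**3. Chance of being called progressed within 28 days of the response.** Assume the remaining transfusions arrive at random (Poisson) at m per 56 days. This is my assumption, not the plan's. Then P = 1 − exp(−m × 28/56):

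- m = 1: 1 − exp(−0.5) = 39%
- m = 2: 1 − exp(−1) = 63%
- m = 4: 1 − exp(−2) = 86%
- m = 6: 1 − exp(−3) = 95%

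**4. Consistency with SAP 5.1.11.** A subject with 56 clear days who later has one transfusion is post-baseline transfusion independent under 5.1.11. Under 5.1.1 the same subject, if a prior responder, has progressed because of transfusion dependence. Section 5.1.1 does not refer to 5.1.11.

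**5. Which endpoints take up the error?**

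- *Primary MDS rate (SAP 6.4.1) and best response (SAP 5.1.5):* both use best response, in which progression ranks last, so a later progression cannot remove a response.
- *ORR (SAP 5.1.6):* counts a response at any post-baseline visit, so it is unchanged.
- *PFS (SAP 5.1.10):* takes progression directly, so it is affected.
- *Duration of response (SAP 5.1.9):* ends at documented relapse, not at progression. "Duration of response for MDS includes duration of CR and duration of response", the latter including BM CR, but relapse is defined only after CR or PR.

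**The case against.** The strongest reply is that the label, transfusion dependence, implies repeated need and not one transfusion. The SAP revision history also names progression and transfusion dependence as the matters clarified in version 3.0, so the wording looks deliberate. The label does leave room for that reading. But the words after it are the only definition in 5.1.1, and they are what a programmer would code. Even on the softer reading, a marrow CR subject with a regular, unchanged need is still dependent and would still be called progressed.

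Four stronger conclusions are tempting, and the documents do not support them:

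- *That the primary MDS result is biased because BM CR is part of it.* A later progression does not cancel a response already counted.
- *That duration of response is cut short.* SAP 5.1.1 says a relapse counts as progression; it does not say progression counts as relapse. Duration is affected only if relapse from BM CR or HI, which is mentioned but never defined, is read through the transfusion criterion.
- *That progression can fall inside the 4 weeks that confirm marrow CR.* The criterion needs a previous response, and the SAP does not say whether marrow CR is dated from the start or the end of those weeks.
- *That every marrow CR subject transfused at baseline is misclassified.* One who stops needing transfusions with the response has no routine transfusion to trigger the rule.

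It is also fair to say that PFS is not among the protocol's endpoints and will not be summarised.

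**Conclusion.** The criterion is wrong as written, with minor impact. For a marrow CR or HI responder still transfused at an unchanged or reduced rate, it dates progression at the next transfusion, and the listed PFS date is then wrong. No planned summary estimate changes. Duration of response, also listing-only (SAP 6.4.2.5), is exposed only through the undefined relapse from BM CR or HI.

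The comparison of definitions needs no assumption beyond reading the criterion as it stands. The 14-day interval assumes single units evenly spaced, and the 39% to 95% range assumes Poisson arrivals at 1 to 6 units per 8 weeks. The documents do not give the share of MDS responders still transfused, so the number of subjects with a wrong date cannot be computed.

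**What to change.** Amend the criterion in SAP 5.1.1:

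1. Remove BM CR without HI from it.
2. Count transfusion as progression only when a subject loses transfusion independence that was present before treatment or gained with the response.
3. For HI by transfusion reduction, count it only when need rises above the level at response.
4. Judge this by lineage (red cells or platelets) from dated transfusion records, with the number of units or episodes and the time window stated.

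The existing SAP 5.1.11 status cannot do this. It pools red cells and platelets, gives one undated status for the whole post-baseline period, and uses a baseline that runs to 28 days after first dose. Reconcile the amended criterion with 5.1.11 and with the CR/PR-only relapse rule, and either define relapse from BM CR and HI or remove the reference to it.

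The cost is SAP wording and reprogramming one derivation, plus a data check. SAP 6.2.5 records transfusions from 28 days before Cycle 1 Day 1 through end of treatment. PFS follow-up continues beyond end of treatment, and the HI-erythroid comparison looks back 8 weeks (56 days). If the records do not cover both, state that limit with the listing.

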### **5.1.2 Secondary Efficacy Endpoint: CR Rate**

CR rate is defined as the number of subjects who achieve CR at any of the postbaseline visits divided by the number of subjects in the analysis population.

### **5.1.3 Secondary Efficacy Endpoint: CRh Rate**

CRh rate is defined as the number of subjects who achieve CRh at any of the postbaseline visits divided by the number of subjects in the analysis population. CRh is applicable for AML subjects only.

### **5.1.4 Secondary Efficacy Endpoint: CR/CRh Rate**

CR/CRh rate is defined as the number of subjects who achieve CR or CRh at any of the postbaseline visits divided by the number of subjects in the analysis population. CR/CRh is applicable for AML subjects only.

### **5.1.5 Secondary Efficacy Endpoint: Best Response Rate**

Best Response Rate is defined as the number of subjects who achieve CRc or PR at any of the postbaseline visits divided by the number of subjects in the analysis population. Best response rate is applicable for AML subjects only.

- Best response for AML subjects is defined as the best measured response to treatment for all visits (in the order of CR, CRp, CRI, PR, NR and NE) postbaseline. Subjects who achieve the best responses of CR, CRp, CRI, or PR will be classified as responders. Subjects who do not achieve at least a best response of PR will be classified as non-responders.
- Best response for MDS subjects is defined as the best measured response to treatment for all visits (in the order of CR, PR, BM CR, HI, SD and PD) post-baseline. Subjects who achieve the best responses of CR, BM CR, or PR will be classified as responders. Subjects who do not achieve at least a best response of PR will be classified as non-responders.

### **5.1.6 Secondary Efficacy Endpoint: Objective Response Rate (ORR)**

Objective Response Rate (ORR) is defined as the number of subjects who achieve CR, BM CR, or PR or HI at any of the postbaseline visits divided by the number of subjects in the analysis population. ORR is applicable for MDS subjects only.

### **5.1.7 Secondary Efficacy Endpoint: Overall Survival (OS)**

OS is defined as the time from the date of first dose until the date of death from any cause (death date – first dose date + 1). For a subject who is not known to have died by the end of study follow-up, OS is censored at the date of last contact (date of last contact – first dose date + 1).

**Table 2 OS Definition**

Situation	Date of Event or Censor	Outcome
Death before or on analysis cutoff date	Date of death	Event
Death after analysis cutoff date	Analysis cutoff date	Censor
Last known alive is before or on cutoff date	Last known alive date	Censor
Last known alive is after cutoff date	Analysis cutoff date	Censor

OS = Date of Event or Censor – Date of first dose +1

### 5.1.8 Secondary Efficacy Endpoint: Event Free Survival (EFS)

EFS is defined as the time from the date of first dose until the date of documented relapse, treatment failure or death from any cause within 30 days after the last dose of IP (whichever occurs first earliest of [relapse date, treatment failure date, death date] – first dose date + 1).

**Table 3 EFS Definition**

Situation	Date of Event or Censor	Outcome
Death or relapse or premature discontinuation of the treatment, or initiation of other anti-leukemic treatment on or before analysis cutoff date	Date of relapse, death, premature discontinuation of treatment or initiation of other anti-leukemic treatment	Event
Death and relapse and premature discontinuation of the treatment and initiation of other anti-leukemic treatment after analysis cutoff date	Last disease assessment date	Censor
No EFS event	Last disease assessment date	Censor
No EFS event and no disease assessment	First dose date	Censor

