#### **ASP7517 Dose/Dose Regimen and Administration Periods**

The study consists of the following periods:

- Screening (up to 14 days)
- Treatment (two 28-day cycles during escalation phase; up to six 28-day cycles during expansion phase)
- End-of-Treatment (EoT) visit
- Post-Treatment
  - Observation Period 1 (12 weeks or until 1 post-treatment discontinuation criterion is met, whichever occurs first)
  - Observation Period 2 (assessment visit every month until 1 post-treatment discontinuation criterion is met)
- Survival and subsequent treatment follow-up every 3 months

During the treatment period, subjects will receive an intravenous infusion of ASP7517 (human embryonic kidney cell transfected with encoding target antigen WT1). In phase 1 (dose escalation), subjects will receive 1 dose per cycle for a total of 2 doses. Each cycle is defined as 28 days with a total of 2 treatment cycles.

In phase 2 (dose expansion), subjects who have not met any individual treatment discontinuation criteria and who are receiving clinical benefit (defined as achieving CRc or PR for AML and CR, BM CR, PR or HI for MDS, or other clinical benefits as determined by the investigator) will continue further treatment with ASP7517 after the first 2 cycles, as decided by the investigator. After completing 4 cycles of treatment, subjects who achieve CR will not continue with ASP7517; subjects who do not reach CR, but also do not experience disease progression, may receive an additional 2 doses for a total of 6 doses. Each cycle is defined as 28 days with a total of up to 6 treatment cycles.

An End-of-Treatment (EoT) visit will be conducted for all subjects within 7 days of the principal investigator decision to discontinue the subject from treatment or prior to the initiation of new anticancer therapy, whichever occurs first. If a subject is completing all visits in the last treatment cycle, the EoT visit will be within 7 days from the last planned visit.

After the EoT visit, Observation Period 1 will be 12 weeks or until 1 post-treatment discontinuation criterion is met, whichever comes first. Subjects who achieve composite complete remission (CRc) or PR for AML and CR, bone marrow (BM) CR or PR or HI for MDS or other clinical benefits, as determined by the investigator, will remain in the study in Observation Period 2 until 1 post-treatment discontinuation criterion is met. Safety and efficacy will be monitored during Observation Periods 1 and 2.

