### 6.4.2.4 Event Free Survival (EFS)

For a subject with none of these events as relapse, treatment failure or death, EFS is censored at the date of last relapse-free disease assessment (last relapse-free disease assessment date – first dose date +1). Subject without post-treatment disease assessment will be censored at randomization date.

Treatment failure includes those subjects who discontinued the treatment due to “progressive disease” or “lack of efficacy” without a previous response of CR, CRp, CRI or PR.

EFS will be presented in listing only.

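### The SAP gives conflicting EFS event rules and two fallback censoring dates, so a subject's event flag and date depend on which section is followed

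*SAP*

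**What the plan says.** The text of SAP 5.1.8 defines EFS as time from first dose to "documented relapse, treatment failure or death from any cause within 30 days after the last dose of IP", whichever is earliest. It does not define treatment failure and gives no censoring rule. Protocol 9.4.2 has the same definition.

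SAP Table 3, directly below that text, lists as an event "Death or relapse or premature discontinuation of the treatment, or initiation of other anti-leukemic treatment on or before analysis cutoff date". It has no 30-day limit on deaths and does not list treatment failure. Subjects without an event are censored at their last disease assessment. For "No EFS event and no disease assessment" the date is first dose.

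SAP 6.4.2.4 begins its censoring rule "For a subject with none of these events as relapse, treatment failure or death", again without the 30-day limit. It then supplies the missing definition: "Treatment failure includes those subjects who discontinued the treatment due to" progressive disease or lack of efficacy, with no earlier CR, CRp, CRi or PR. Its fallback is different: "Subject without post-treatment disease assessment will be censored at randomization date".

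The SAP presents EFS as a listing only (6.4.2.4). Protocol 9.4.2 still calls for a Kaplan-Meier estimate at each dose level. Neither document says which EFS rule governs.

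**The concern.** Even a listing needs one event flag and one date per subject, and a programmer following these sections in good faith could produce different listings. The rules also pull in opposite directions. Leaving out deaths more than 30 days after the last dose lengthens EFS, while counting every premature stop and every new therapy shortens it. In an open-label study, a rule settled after the data have been seen would be a post hoc choice.

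The 30-day limit is not a rare technicality. Dosing is on day 1 of each 28-day cycle. For a subject whose last dose is in cycle 2, the dose falls on study day 29 and the window closes on day 29 + 30 = 59, three days after the cycle ends on day 56. A death without earlier relapse or treatment failure in nearly all of Observation Periods 1 and 2 would then not be an event under the 5.1.8 text. Protocol 2.3 describes survival measured in weeks for some of these AML patients, and a median under 6 months for MDS after standard treatment has failed, so such deaths are plausible.

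Table 3 also leaves premature discontinuation undefined. SAP 2.2 says "After completing 4 cycles of treatment, subjects who achieve CR will not continue with ASP7517", although up to six cycles are allowed. Table 3 does not say that such a stop is excluded.

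**Working it through.** The documents give no sample size, power or event count for EFS, so there is no figure to reproduce. The check sets the rules side by side and applies them literally to the same hypothetical subjects.

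**Rules**

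| Situation | 5.1.8 text | Table 3 | 6.4.2.4 |
|---|---|---|---|
| Relapse | event | event | event |
| Treatment failure | event, undefined there | not listed | event, defined |
| Death 30 days or less after last dose | event | event | event |
| Death later than that | not an event | event | event, no limit stated |
| Premature stop for an adverse event | not listed | event | not an event |
| New anti-leukemic therapy | not listed | event | not listed |
| No event, assessed | no rule | last assessment | last relapse-free assessment |
| No event, not assessed | no rule | first dose date | randomization date |

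**Who has a randomization date.** SAP 2.3 describes random allocation only in phase 2, and only while more than one dose level is open within a disease type. Phase 1 subjects, and phase 2 subjects enrolled with one level open, have none.

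**Application.** First dose is day 0 and EFS = date − first dose date + 1. Where several Table 3 events occur, the earliest is used.

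| Hypothetical subject | 5.1.8 text | Table 3 | 6.4.2.4 |
|---|---|---|---|
| A. Last dose day 28, stops for adverse event day 40, last assessed day 28, alive, no relapse | no event, no censoring rule | event, 40 + 1 = 41 | censored, 28 + 1 = 29 |
| B. Responder stops day 58 (taken as premature), new therapy day 60, last assessed day 56, no relapse | no event, no censoring rule | event, 58 + 1 = 59 | censored, 56 + 1 = 57 |
| C. Last dose day 28, dies day 120 without relapse or treatment failure | 120 − 28 = 92 > 30, not an event | event, 120 + 1 = 121 | event, 121 |
| D. Last dose day 28, stops for adverse event day 40, dies day 120 | not an event (92 > 30) | event, 41 | event, 121 |
| E. Phase 1, withdraws day 10, never assessed after baseline | no event, no censoring rule | event, 10 + 1 = 11 | no date exists |
| F. Phase 1, no event, never assessed | no rule | censored, 0 + 1 = 1 | no date exists |
| G. Randomized 1 or 3 days before first dose (assumed gaps), no event, never assessed | no rule | censored, 1 | −1 + 1 = 0, or −3 + 1 = −2 |

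Subject A is an event, censored or without a rule, depending on the section. Subject C separates the 5.1.8 text from the other two. Subject D is an event under both Table 3 and 6.4.2.4, 80 days apart (121 − 41). Subject G shows that a randomization fallback can give a zero or negative time, because time runs from first dose.

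**The case against.** The strongest reply is that 6.4.2.4 does not compete with 5.1.8. It names the same three events and supplies the definition of treatment failure that 5.1.8 lacks, so the two form one definition and Table 3 is the outlier. That reading is fair. A reader might infer three incompatible definitions, but the third exists only if the missing 30-day limit in 6.4.2.4 is taken literally. The conflict with Table 3 remains on either reading.

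Other stronger inferences are not supported:

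- **Two time origins.** EFS is counted from first dose throughout. Only the fallback censoring date differs.
- **Most subjects lack a randomization date.** The documents do not give the number of phase 2 dose levels, so the share is unknown. The SAP also pairs randomized with allocated or assigned elsewhere, so loose wording is plausible. It still leaves phase 1 without a usable date.
- **A definite number of subjects switching status.** If 10% to 30% stopped for reasons other than progression or lack of efficacy, that would be 0.10 × 52 = 5.2 to 0.30 × 52 = 15.6 subjects per cohort. The percentages have no source in the documents. Fifty-two is a maximum, and a cohort that stops at 12 gives 1.2 to 3.6. Some of these subjects, like D, change only in date.
- **CR after four cycles is counted as failure.** Such a stop is protocol-directed and is not among the discontinuation criteria in protocol 8.1.1. Table 3 leaves room for the misreading but does not require it.

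The 6.4.2.4 response list also omits marrow CR and hematologic improvement (HI), which matter for MDS. Simply adding them would do harm. An MDS subject with either response who stops for progression is now a treatment failure, hence an event. With the list extended, that subject would no longer be one, and MDS relapse criteria are given only after CR or PR.

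**Conclusion.** The point holds: the EFS rules are wrong as written and should be corrected. There are at least two incompatible event definitions and two fallback censoring dates, one of which does not exist for some subjects. Following the stated rules changes both flags and dates. The number of subjects affected cannot be derived from the documents.

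The consequence is limited. EFS is listing-only in the SAP, no test or power statement depends on it, and the BOP2 decisions use response. The ambiguity would matter more if the Kaplan-Meier estimate still specified in the protocol were produced.

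The conclusion assumes that the sentence in 6.4.2.4 on treatment failure is a definition and not a list of examples. If it were only examples, subject A would be unresolved there too, and the need for one rule would be the same.

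**What to change.** Before database lock, use one definition in SAP 5.1.8, Table 3, SAP 6.4.2.4 and protocol 9.4.2:

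- **Event:** the earliest of relapse, treatment failure as defined in 6.4.2.4, or death from any cause with no 30-day limit.
- **MDS:** if marrow CR and HI are added as prior responses, also count progression or relapse from them as an event, using the progressive-disease criteria in SAP 5.1.1, so that progression is not lost.
- **New anti-leukemic therapy:** state one rule. An example is censoring at the last assessment before it starts, as Table 4 does for PFS.
- **Stopping in CR as the protocol directs:** state that, for EFS, this is not premature discontinuation.
- **Censoring:** at the last relapse-free assessment, or at first dose if there is none. Delete the reference to a randomization date.

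The cost is wording in the SAP and in protocol 9.4.2, where the 30-day limit also stands, or a documented SAP departure from the protocol text. No new data are needed.
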